1. REPORTING & ANALYSIS PLAN SYNOPSIS

Overview	Key Elements of the RAP
Purpose	
The purpose of this RAP is to describe:
 
 • An informal interim analysis, so as to provide project team and GSK stakeholders with key data to inform internal decision making, in order to start the Part B and C (cold urticaria and spontaneous urticaria subjects) of this study. • This RAP will be provided to the study team members to convey the content of the [Reference as Required: Statistical Analysis Complete (SAC)] deliverable.
Protocol	
 • This RAP is based on the protocol amendment 2 [(Dated: 10/DEC/2014) of study GSK2646264 (GSK Document Number: 2013N167482_01] and eCRF Version (Version 1, 09OCT2014).
Primary Objective	
 • The primary objective is to investigate the safety and tolerability of topically applied GSK2646264 cream and its placebo in healthy subjects, subjects with cold urticaria (CU) and subjects with chronic spontaneous urticaria (CsU)
Primary Endpoint	
 • Safety and Tolerability (Number, severity and frequency of AEs and serious AEs (local and systemic), heart rate, blood pressure, 12- lead ECG, clinical laboratory safety tests, assessment of the local tolerability of the study medication
Study Design	
 • Randomised, double blind (sponsor unblinded), bilateral, single and repeat ascending dose First Time in Human study in healthy subjects, cold urticaria and chronic spontaneous urticaria subjects. • Approximately 18 randomised evaluable subjects in Part A, and approximately 12 randomised evaluable subjects in part B and C of study.
Planned Analyses	
 • Safety and Tolerability, PK, PD (Allergen challenge, UAS7, AAS), Health Outcome (DLQI)
Analysis Populations	
 • Primary: Safety population, • Other: PK, PD, Per-Protocol populations
Hypothesis	
 • There are no formal hypotheses being tested in the study; instead an estimation and inference approach will be adopted to evaluate the objectives.
Primary Analyses	
 • Safety data will be presented in tabular and/or graphical format and summarized descriptively according to GSK's Integrated Data Standards Library (IDSL) standards.
Secondary Analyses	
 • Individual GSK2646264 plasma concentration-time profiles and median/mean (\pmSD) profiles will be plotted and listed. Plasma concentration time data for GSK2646264 will be analyzed by non-compartmental methods using WinNonlin and derived PK parameters (AUC, C_{max}, T_{max}, t_{1/2}) summarized, listed and plotted. No formal statistical analyses will be conducted.
Exploratory Analyses	
 • All PD endpoints will be summarized, listed and graphically presented. Where

Overview	Key Elements of the RAP
	applicable, Paired t-Tests and/or ANCOVA model will be performed. Point estimates, and 95% confidence interval will be provided.

2. SUMMARY OF KEY PROTOCOL INFORMATION

2.1. Changes to the Protocol Defined Statistical Analysis Plan

The following changes or deviations to the originally planned statistical analysis specified in the protocol [(Dated: 10/DEC/2014)].

- Study endpoints were modified for Part A of the study as some of the data points mentioned in original planned protocol analyses were not feasible to obtain via method and equipment used in the study.
- After Dose escalation meeting (at the end of dose group 1), dosing of dose group 2 in Part A study was modified. In a new design, subjects will be dosed up to 4 days only and up to a maximum BSA level of 10% in order to further understand the elimination phase of the systemic drug concentration. Therefore, all analyses will be carried out using new dosing plan.

2.2. Study Objective(s) and Endpoint(s)

Objectives	Endpoints
Primary Objectives	Primary Endpoints
Part A, B and C	Part A, B and C

 • To investigate the safety and tolerability of topically applied GSK2646264 cream and its placebo in healthy¹ subjects, subjects with cold urticaria (CU¹) and subjects with chronic spontaneous urticaria (CsU). 	
 • Number, severity and frequency of AEs and serious AEs (local and systemic) • Heart rate • Blood pressure • 12- lead ECG • Clinical laboratory safety tests • Assessment of the local tolerability of the study medication
Secondary Objectives	Secondary Endpoints
Part A, B and C	Part A, B and C

 • To evaluate the plasma concentrations of GSK2646264 in Healthy, CU and CsU subjects 	
 • Plasma concentrations of GSK2646264 and pharmacokinetic parameters, including AUC, C_{max}, T_{max}, t_{1/2}, if data allows
Exploratory Objectives	Exploratory Endpoints
Part A: Healthy Subjects	Part A: Healthy Subjects

 • Assess the pharmacodynamic effect of GSK2646264 on weal and flare sizes and erythema, in healthy subjects after allergen challenge (Skin Prick test, positive control (histamine) and negative control (Saline)). • Duration of response in healthy subjects 	
 • Percent inhibition on days 1, 3, 4 and 6⁶ for the longest weal diameter (measured by ruler). • Percent inhibition on days 1, 3, 4 and 6⁶ for perpendicular weal length (measured by ruler). • Percent inhibition on days 1, 3, 4 and 6⁶ for weal area (calculated⁵). • Percent inhibition on days 1, 3, 4 and 6⁶ for Weal volume (measured by quantitative volumetric morphometry²) • Percent inhibition on days 1, 3, 4 and 6⁶ for Flare erythema (measured by Mexameter³). 
Percent of inhibition at 48 hours post final dose, will be derived for the endpoints above

Objectives	Endpoints
Part B: Cold Urticaria Subjects	Part B: Cold Urticaria Subjects

 To assess the pharmacodynamic effect of GSK2646264 on weal and flare sizes and erythema, in cold urticaria subjects after allergen challenge (Skin Prick test, positive control (histamine) and negative control (Saline)). 	
 Percent inhibition on days 1, and 3 for the longest weal diameter (measured by ruler). Percent inhibition on days 1, and 3 for perpendicular weal length (measured by ruler). Percent inhibition on days 1, and 3 for weal area (calculated). Percent inhibition on days 1, and 3 for Weal volume (measured by quantitative volumetric morphometry¹) Percent inhibition on days 1, and 3 for Flare erythema (measured by Mexameter²).

 To assess the effect of GSK2646264 on Cold Temperature Test values 	
 Change in Cold Temperature Test⁴ values at day 1 and day 3
Part C: Chronic Spontaneous Urticaria Subjects	Part C: Chronic Spontaneous Urticaria Subjects

 To assess the effect of GSK2646264 on weal characterisation in CsU subjects within treated area only To assess the Quality of Life in CsU subjects. To assess the disease activity in CsU subjects. To investigate the relationships between (basophil histamine release) BHR test and weal characteristics 	
 Urticaria Activity Score, a composite score using key urticaria symptoms (number of weals, Itch/Pruritus), to derive change from baseline on Day 1 through to Day 7 Change from baseline in total Dermatology Life Quality Index (DLQI) score Change from baseline in Angioedema Activity Score (AAS) Relationship of positive BHR test with reduction in number or size of weals
1 All Healthy subjects and the Cold Urticaria subjects should be screened for reactivity to one of the allergens used in skin prick test. (grass pollen, Dermatophagoïdes pteronyssinus, birch pollen and cat dander) 2 Measured using digital camera using PRIMOS 5.075D instrument software produced by GMF 3 Measures erythema and melanin index values using narrow band spectrophotometry 4 TEMPTest 4.0 5 Calculated as ellipse or oval area	

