Treatment Assignment	
 Subjects will participate in the study if they fulfil the eligibility criteria at the time of screening and prior to randomisation for the relevant cohort for which they are assessed. This is the first clinical application for GSK2646264 in any formulation and therefore first exposure in each part of the study will enroll 1 sentinel subject for: 
 Part A dosing group1

Overview of Study Design and Key Features	
	
 ○ Part A dosing group 2 ○ Part B ○ Part C 
Each sentinel subject will be dosed at least 1 day before any other subjects of their dosing group or cohort.
 
 ● Subjects will be assigned to treatment in accordance with the randomization schedule using IVRS system. Randomisation will occur within each cohort of study. Each subject will be randomised to receive bilateral treatment of GSK2646264 or placebo. Randomisation will assign active and placebo to specified areas on left or right side of the body. The left or right side assignment of treatment always refers to the subject's left or right.
Interim Analysis Informal data review	
 ● No formal interim analyses are planned. ● An informal summary of the safety, tolerability, PK and PD data from Part-A will be performed once all subjects are recruited and completed all visits.

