11.3. Appendix 3: Data Display Standards & Handling Conventions

11.3.1. Study Treatment & Sub-group Display Descriptors

Treatment Group Descriptions			
RandAll NG		Data Displays for Reporting	
Code	Description	Description	Order ^[1]
A	GSK2646264 X.X mg	GSKX.X mg	2
P	Placebo	Placebo	1

NOTES:

1. Order represents treatments being presented in TFL. Placebo is to be presented at start in Tables, Figures and Listings. Dosing of GSK treatment will be displayed in ascending order, where appropriate.

In accordance with the body surface area (BSA) to be used Arm, Leg and Front Torso of the subjects had to be treated on the different body sides with either GSK2646264 or matching placebo treatment as displayed below:

Table 11 Overview of Treatments Doses and Analyses.

Part	Dose	BSA treated per body side (left/right)	Day of Treatment (Tests performed)	Comment
A	0.5% (Group 1)	0.2% 1% 5%	D1 (PK/PD) D2 (PK) D3 (PK/PD)	qd
A	1.0% (Group 2)	5% 5% 10% 10%	D1 (PK/PD) D2 (PK) D3 (PK/PD) D4 (PK)	qd
B	.0.5 or 1%	0.2%+5% 0.2%+5% 0.2%+5%	D1(PK/PD) D2 D3(PK/PD)	qd or bid (D3 morning dose only)
C	.0.5 or 1%	X.X2%	D1 (PK/PD) D2 (PD) D3 (PD) D4 (PK/PD) D5 (PD) D6 (PD) D7 (PK/PD)	Qd or bid

¹ maximum tolerated dose (taken from Part A)

² maximum BSA treated (taken from Part A)

The following changes to treatment dosing were made to dose group 2 (Part A) in light of dose escalation review meeting at the end of dose group 1:

Table 12 Treatment applied to specified areas per day on Part A; healthy subjects, n=9, dose group 2

	Day 1-2	Day 3-4	Day 5 to 7
Area	AM ^a	AM ^a	
Left Arm	0.36g of 1.0% ^b GSK2646264 or placebo cream applied to 36cm ² (~0.2% BSA)		NO DOSING
Right Arm	0.36g of 1.0% ^b GSK2646264 or placebo cream applied to 36cm ² (~0.2% BSA)		NO DOSING
Left Front Torso	9g of 1.0% ^b GSK2646264 or placebo cream applied to 900cm ² (~5% BSA)	18g of 1.0% ^b GSK2646264 or placebo applied to 1800cm ² (~10% BSA)	NO DOSING
Right Front Torso	9g of 1.0% ^b GSK2646264 or placebo applied to 900cm ² (~5% BSA)	18g of 1.0% ^b GSK2646264 or placebo applied to 1800cm ² (~10% BSA)	NO DOSING

a. AM dosing only

b. 0.5% strength may be used if data for Part A and/or group 2 supports

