11.3.2.2. Derivations and Handling of Missing Baseline Data

Definition	Reporting Details
Change from Baseline	= Post-Dose Visit Value – Baseline
% Change from Baseline	= $100 \times [(Post-Dose Visit Value - Baseline) / Baseline]$
% inhibition	= $[(control - treatment)/control] \times 100$

NOTES :

- Unless otherwise specified, the baseline definitions specified in Section 11.3.2.1 Baseline Definitions will be used for derivations for endpoints / parameters and indicated on summaries and listings.
- Unless otherwise stated, if baseline data is missing no derivation will be performed and will be set to missing.
- As only one baseline will be defined for all parameters (i.e. at the start of the study), there will only be one baseline on all summaries (i.e. not a separate baseline for each subsequent repeat dose).
- The baseline definition will be footnoted on all change from baseline outputs, where applicable.
- If baseline value for (day -1) is missing, screening value will be used as baseline. If both assessments are missing then no derivation will be performed and will be set to missing..

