11.10.3. Deliverable [Priority]

Delivery [Priority] ^[1]	Description
IA [X]	Interim Analysis Statistical Analysis Complete
SAC [X]	Final Statistical Analysis Complete

NOTES:

- Indicates priority (i.e. order) in which displays will be generated for the reporting effort.

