11.10.11. Pharmacodynamic Figures

Pharmacodynamic : Figures					
No.	Population	IDSL / TST ID / Example Shell	Title	Programming Notes	Deliverable [Priority]
Pharmacodynamics					
5.1.	PD	Non-Standard _PD_F1	Allergen Challenge, Weal Area (Percent of Inhibition) - Individual Subject Plot	Part A + B Page by : Treatment X-Axis : Continuous scale for visit (days) Y-Axis : Scaled accordingly to Parameter and include parameter name Legend : Subject	SAC [1]
5.2.	PD	Non-Standard _PD_F2	Allergen Challenge, Weal Area (Percent of Inhibition, absolute value) - Box Plot	Part A + B X-Axis : Days Y-Axis : Result Legend : Treatment	SAC [1]

Pharmacodynamic : Figures					
No.	Population	IDSL / TST ID / Example Shell	Title	Programming Notes	Deliverable [Priority]
5.3.	PD	Example Non-Standard _PD_F1	Allergen Challenge, Weal Volume (Percent of Inhibition) - Individual Subject Plot	Part A + B Page by : Treatment X-Axis : Continuous scale for visit (days) Y-Axis : Scaled accordingly to Parameter and include parameter name Legend : Subject	SAC [1]

Pharmacodynamic : Figures					
No.	Population	IDSL / TST ID / Example Shell	Title	Programming Notes	Deliverable [Priority]
5.4.	PD	Example Non-Standard _PD_F2	Allergen Challenge, Weal Volume (Percent of Inhibition, absolute value) - Box Plot	Part A + B X-Axis : Days Y-Axis : Result Legend : Treatment	SAC [1]
5.5.	PD	Example Non-Standard _PD_F1	Allergen Challenge, longest weal Diameter (Percent of Inhibition) - Individual Subject Plot	Part A + B Page by : Treatment X-Axis : Continuous scale for visit (days) Y-Axis : Scaled accordingly to Parameter and include parameter name Legend : Subject	IA[1],SAC [1]
5.6.	PD	Example Non-Standard _PD_F2	Allergen Challenge, longest Weal Diameter (Percent of Inhibition, absolute value) - Box Plot	Part A + B X-Axis : Days Y-Axis : Result Legend : Treatment	IA[1],SAC [1]

Pharmacodynamic : Figures					
No.	Population	IDSL / TST ID / Example Shell	Title	Programming Notes	Deliverable [Priority]
5.7.	PD	Example Non-Standard _PD_F1	Allergen Challenge, Weal perpendicular length (Percent of Inhibition) - Individual Subject Plot	Part A + B Page by : Treatment X-Axis : Continuous scale for visit (days) Y-Axis : Scaled accordingly to Parameter and include parameter name Legend : Subject	IA[1],SAC [1]
5.8.	PD	Example Non-Standard _PD_F2	Allergen Challenge, Weal perpendicular length (Percent of Inhibition, absolute value) - Box Plot	Part A + B X-Axis : Days Y-Axis : Result Legend : Treatment	IA[1],SAC [1]

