Programming Notes : [1] As required to be modified based on data and any applicable IDSL standard principals for listings

Example : Non-Standard _PD_F1
Protocol : 2013N167482_01
Population : PD

Page 1 of X

Figure 5.1
Allergen Challenge, Weal Area (Percent of Inhibition) - Individual Subject Plot

[figure not shown]

Programming Notes : [1] Plot adapted accordingly based on study data (overlaid by treatment)
[2] Subject will have two values one for treatment and another for placebo. Therefore use one colour for the subject id and two symbols for treatment (e.g. o=placebo, +=Treatment). Adapt the graph correspondingly.

Example : Non-Standard _PD_F1
Protocol : 2013N167482_01
Population : PD

Page 1 of X

Figure 5.2
Allergen Challenge, Weal Area (Percent of Inhibition) - Mean (95% CI) Plot

Programming Notes : [1] Plot adapted accordingly based on study data.
[2] Replicate this box plot to other similar plots, eg. for absolute values..

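### Part B pharmacodynamics: the SAP still assumes bilateral treatment, so the control for percent inhibition is unspecified, Day 1 counts as an effect day although it is now pre-dose, and the cold-test baseline is inconsistent

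*SAP*

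**What the plan says.** **Design assumed by the SAP.** Section 1 names its source: "This RAP is based on the protocol amendment 2", dated 10 December 2014. Section 2.3 describes allocation without separating the parts: "Each subject will be randomised to receive bilateral treatment of GSK2646264 or placebo". Section 11.3.1 has body areas "treated on the different body sides with either GSK2646264 or matching placebo treatment", and its Table 11 gives Part B a row of BSA per side. Section 2.1 lists departures from the protocol for Part A only.

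**Skin prick.** Section 2.2 has "Percent inhibition on days 1, and 3 for the longest weal diameter (measured by ruler", with the same days for the other four skin-prick measures. Section 11.3.2.2 defines percent inhibition by the expression "control - treatment)/control", scaled to 100, and leaves control undefined. The baseline table in Section 11.3.2.1 records that there is none. Section 11.10.11 lists Figure 5.1, "Allergen Challenge, Weal Area (Percent of Inhibition) - Individual Subject Plot", for Parts A and B together. The mock Figure 5.1 in Section 11.11 carries the note "Subject will have two values one for treatment and another for placebo".

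**Cold test.** Section 2.2 asks for change at Days 1 and 3. The baseline table again records none. The note to Table 7 (Section 9.1.1) and Figure 5.12 call for a change but give no reference value. Table 5.6 has change in its title and absolute values in its programming note. Listing 32 asks for change from baseline.

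Table 5.6, Figure 5.12 and Listing 32 cover Part B alone and are marked for the deliverable that Section 11.10.3 describes as "Final Statistical Analysis Complete".

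**Current protocol.** Sections 3.2.1 and 5.4 make Part B parallel, 3:1, with one treatment per subject. Section 6.1.3 schedules both tests before dosing on Day 1, at 6 hours after the Day 3 dose, and 24 hours after the last dose. Section 2.3.2 places both endpoints at Day 3. It names no control for percent inhibition and expresses the cold-test endpoint relative to placebo.

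**The concern.** In a bilateral trial, percent inhibition has a natural control: the placebo-treated side of the same subject. That explains why the SAP could do without a baseline and expect two values per subject. Once Part B became parallel, that control disappeared and nothing replaced it. The former Day 1 skin-prick test, 6 hours after dosing in the SAP's own schedule (Section 11.2.1.3), also became a pre-dose test, while Section 2.2 kept Day 1 as an effect day.

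Protocol Section 3.2.1.2 expects these two tests to show target engagement in Part B. Followed literally, the SAP would report a pre-treatment reading as an effect and leave the programmer to choose the control. The sponsor is unblinded and SAP Section 3.1 provides for continuing review of unblinded pharmacodynamic data, so a control left open could be chosen after the results are known.

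**Working it through.** **1. The plan's own figure.** The documents give no precision for Part B. The only figure for percent inhibition is Part A's (Protocol Section 9.2.1): half-width 18.5 with n = 9 and SD 24. It reproduces as t(0.975, 8) × 24/√9 = 2.306 × 8 = 18.45. That is a within-subject interval, so it belongs to the bilateral design and does not carry over to Part B.

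**2. Version.** The SAP rests on Amendment 2. The protocol's revision chronology shows that Amendment 3 (June 2015) made Parts B and C parallel. The current protocol is Amendment 5.

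**3. Pairs available.** Twelve subjects at 3:1 gives 12 × 3/4 = 9 active and 3 placebo. Each receives one treatment, so subjects with both an active and a placebo value number 0 of 12. Skin prick is done only in subjects positive at screening. Protocol Section 4.2.1.3 sets a minimum of 4, so the relevant count lies between 4 and 12, with 0 pairs throughout.

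**4. What control could mean.**
- *The subject's own placebo side:* does not exist in Part B.
- *The placebo-arm mean:* computable if at least one placebo subject is prick-positive. If positivity is unrelated to arm (an assumption) and K of the 12 are positive, the chance that none is on placebo is C(9,K)/C(12,K). For K = 4 this is 126/495 = 25%; for K = 6, 84/924 = 9%; for K = 8, 9/495 = 2%.
- *The subject's own Day 1 pre-dose value:* scheduled for every subject tested, but the SAP's baseline table excludes it.
- *The histamine positive control:* a possible reading of the word, since Protocol Section 6.4.1 keeps it in use during dosing. Nothing in the SAP adopts it.

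The second and third are different quantities, and neither document chooses between them.

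**5. Day 1.** SAP Section 2.2 makes it an effect day for both tests. Protocol Section 6.1.3 puts both before the first dose. A Day 1 inhibition or change therefore contains no treatment effect.

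**6. Cold test.** The baseline table and Listing 32 cannot both be followed. The general SAP rule, that baseline is the latest pre-dose value, does not settle it, because that rule yields to exceptions and the table makes the cold test one.

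**7. Precision, as context only.** The pooled equal-variance 95% half-width for active minus placebo, in SD units, is t(0.975, n1+n2−2) × √(1/n1 + 1/n2).
- All 12 subjects, 9 v 3: 2.228 × 0.6667 = 1.49 SD.
- The last 8 at 3.5% BSA, 6 v 2 if 3:1 holds: 2.447 × 0.8165 = 2.00 SD.
- The first 4 at 10% BSA, 3 v 1: 4.303 × 1.1547 = 4.97 SD, with a single placebo value, so equal variance cannot be checked.

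These describe the small placebo arm. They do not measure the wording problem, and correcting the wording leaves them unchanged.

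**The case against.** **The SAP is simply older than the design change.** It matches Amendment 2, its stated purpose includes an informal review before Parts B and C, and a later version may exist. This stands in part: the missing control and the Day 1 problem are one failure to update, not separate analytical errors. But no later version was supplied, and this one specifies Part B displays for the final analysis. The cold-test inconsistency does not depend on the SAP's age.

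**Percent inhibition is not lost.** A reader might infer that it cannot be derived at all in Part B. The documents do not support that. Protocol Section 9.1.1 and SAP Section 11.8.1 both name placebo as the comparator, so an arm-level value is computable whenever a placebo subject is prick-positive. What is missing is the level at which control is defined. The note about two values per subject is also only a programming note, and the shell allows adaptation to the data.

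**The cold-test conflict is narrow.** A change relative to placebo needs no baseline, and the protocol's endpoint can be read as a between-arm contrast. That is fair: the direct contradiction rests mainly on the Listing 32 note, and the Table 5.6 note may be a display slip, since Table 7 asks for both absolute values and change. The reference for the change is still unstated.

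**Own pre-dose inhibition differs from Part A's measure,** although SAP Tables 5.1 to 5.5 show both parts under one title. This stands, and calls for a label.

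**Other evidence remains.** Absolute summaries by treatment are unaffected, and CD69 is a further pharmacology measure in Part B.

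**Conclusion.** The concern holds as a failure to carry the parallel design into the SAP's Part B pharmacodynamic rules. The control for percent inhibition is not specified, Day 1 is wrongly kept as an effect day, and the cold-test baseline and change do not agree. This should be settled before Part B is analysed.

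Its reach is limited. These are exploratory, descriptive endpoints with no formal testing (Protocol Sections 2.3.2 and 9.3.2.3.1), and neither the primary safety analysis nor the sample size depends on them. The textual findings need no assumption beyond treating the supplied SAP as the one in force. The chances in step 4 assume a number of positives and independence from arm; the documents give only the minimum of 4. A reader might take the wide half-widths as evidence of the defect, but they follow from about 3 placebo subjects and would be the same under a corrected SAP.

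**What to change.** In the SAP, for Part B:

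- Remove Day 1 as an effect time point and make the Day 1 pre-dose reading the baseline for both tests. Report Day 3 at 6 hours and the 24-hour reading.
- Define cold-threshold change as post-dose minus Day 1 pre-dose.
- Name one control for percent inhibition before the Part B data are analysed. The subject's own Day 1 pre-dose value is suggested, giving 100 × (pre-dose − post-dose)/pre-dose, summarised by arm and BSA. It exists for every subject tested, whereas the placebo-arm mean may not. Label it as a different quantity from the Part A side-to-side inhibition.
- Correct the two baseline-table rows, the note on paired values in the mock Figure 5.1 as it applies to Part B, and the notes to Table 5.6 and Listing 32, so that all agree.
- Treat any active-minus-placebo contrast as optional and descriptive, and note that it is very imprecise with about 3 placebo subjects.

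The cost is SAP text and a few display notes. The Day 1 pre-dose, Day 3 and 24-hour readings are already scheduled, so no procedures or subjects are added. The protocol names no control, so naming one in the SAP contradicts nothing there.
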